#### 5.3.8 **Prohibited medications**

For study day 1-15, use of medications, including off-label, expanded access, or investigational agents, with potential anti-COVID-19 activity should not be administered. These include the following:

- Hydroxychloroquine or chloroquine
- Lopinavir/ritonavir (unless already prescribed for HIV infection)
- IL-6 receptor antagonists
- High dose corticosteroids initiated for COVID-19 treatment, and not for another indication

If there is uncertainty about possible anti-COVID-19 activity, the medication being used should be discussed with the team. This list will be revised as new data to support or refute efficacy become available.

Note: Azithromycin administered for treatment of presumed or confirmed infection will be permitted.

After study day 15 or in participants who have reached the study endpoint of severe hypoxemia, use of additional anti-COVID-19 treatments such as dexamethasone for those with persistent severe COVID-19 are permitted but should be recorded.

# 5.4 Study procedures

#### Table 1: Schedule of Evaluations

Study period	Screen	Enrollment	Transfusion (within 24 hours of randomization)	Follow up					
Day	Within 3d prior to enrollment	1 (values within 24 hours prior to enrollment)	1	2	5	8	15	29	120
Visit window					+/-	1 day		+/- 7d	+/- 14d
Eligibility									
Informed consent	Х								
Demographic and Medical history	x								
COVID-19 symptom screen	x								
SARS-CoV-2 RT- PCR for eligibility	within 14								
Pregnancy test	days -								
ABO for plasma compatibility	x								
Chest imaging (CXR or CT scan)	х								
Oxygenation Status	х	Х							
		Study I	Drug Administration						
Randomization		Х							
Drug infusion			Х						
Study Procedures									
Vital signs		Х	XXX 		ily days		x 		
Oxygenation status		Х		d	aily 2-8	3 	х	х	Х

Symptom screen	Х	Х	x	x	х	х	х	х	x
Day	Within 3d prior to enrollment	Enrollment (values within 24 hours prior to enrollment)	Plasma transfusion	2	5	8	15	29	120
Visit window				+/-1 day				+/- 5d	+/- 14d
Concomitant medications		x		x	x	x	(only	x COVID t related	reatment 1)
Assessment with 8- point ordinal scale		x		x	х	х	х	x	x
Assessment with WHO 11 point ordinal scale							x	x	
Chest imaging (CXR or CT scan) 					х		х		
Laboratory testing									
CBC (with absolute lymphocyte count)		х		x 	Х 	Х 	X 	X 	х
Renal function, liver function test		х		x 	Х 	Х 	X 		
PT, PTT, D-dimer, hsCRP, ferritin		х		x 	x 	X 	x 	x 	x
SARS-CoV-2 RT- PCR(NP/MTN swab) 		х		x	X 	X 	x 		
Blood for future testing (includes SARS-CoV-2 Ab) 		Х			x 	x 	x 	X 	X 

Vital sign testing, immediately prior to infusion, 10-20 minutes after start of infusion, at completion of infusion and 30-60 minutes after the end of the infusion, ideally bundled with other required clinical care.  If still hospitalized.

 Record most recent preceding chest imaging, if available and conducted per standard of care
  Record lab values if collected as part of standard of care. Will encourage clinical teams to collect but will not be required.
  Blood drawn if in-person visit is feasible

Prioritize day 1 research blood collection and nasal swab. Collect on day 5, 8, 15 if feasible

CAPRI AUAPLIVE PIOLOCOL VEL 5.0 7/20/2020

# STUDY PROCEDURES

# 1. Study Protocol by Day:

### Day -2 to 1:

- A. Screening (must be completed before randomization)
- B. Informed consent (obtained before performing study related activities)
- C. Baseline Evaluation (at screening) (much of the information will be obtained from the medical record)
  - 1. Demographics: Age, sex, race
  - 2. Medical history:
    - Timing of exposure to COVID-19 source patient
    - Acute and chronic medical conditions that a risk factors for COVID
    - Medications, allergies
    - Any medical condition arising after consent to be recorded as AE.
  - 3. COVID-19 symptom screen: Fevers, cough, shortness of breath.
  - 4. History of illness: Onset of symptoms
  - 5. Vital signs
  - 6. Oxygenation status: current FiO2 or liters of O2, route of oxygen support, and oxygen saturation or Pa02 (if available)
  - 7. COVID-19 testing (RT-PCR) Per standard of care. Positive test PCR required within 14 days of screening
  - 8. Baseline Basic Lab Testing
    - ABO Blood typing, CBC with absolute lymphocyte count, comprehensive metabolic panel, inflammatory and coagulation markers (d-dimer, hsCRP, PT/INR, PTT)
  - 9. For females of childbearing potential, urine or serum pregnancy test
    - Results from laboratory tests obtained up to 14 days before enrollment may be used for the pregnancy test
- D. Determination of eligibility
  - Inclusion/exclusion criteria age
  - Consent
  - Positive for COVID-19 within past 14 days
  - not already an ICU patient
  - Within 14 days of first sign of illness or within 72 hours of admission

#### Day 1:

- 1. Randomization of eligible subject
- 2. Study Plasma Administration:
  - 1 unit of plasma will be transfused within 24 hours of enrollment
  - Time at start and end of infusion will be recorded
  - Vital signs will be measured immediately prior to infusion, 10-20 minutes after start of infusion, at completion of infusion and 30-60 minutes after the end of the infusion
- 4. Assessment of clinical status (8-point ordinal scale)
- 5. New medical conditions, concomitant medication, AE evaluation

7. Oxygenation status: current FiO2 or liters of O2, route of oxygen, and oxygen saturation or PaO2 (if available)

8. COVID-19 testing (RT-PCR): nasopharyngeal samples

10. Stored samples for future studies (3 EDT tubes and 1 SST). This will include serological testing for SARS CoV-2 antibodies

# Day 2-15 (if remain hospitalized)

1. Vitals signs (day 2-8)

- 3. Assessment of clinical status (8-point ordinal scale) (days 2,5,8)
- 4. New medical conditions, concomitant medications, AE evaluation (days 2,5,8)

6. Oxygenation status: current FiO2 or liters of O2, route of oxygen, and oxygen saturation or PaO2 (if available) (days 1-8)

7. Nasopharyngeal or mid-turbinate nasal swabs, if feasible (days 2,5,8)

8. Stored samples for future studies(3 EDT tubes and 1 SST) (day 5, 8 only) if feasible. This testing includes SARS-CoV-2 antibody testing

10. CXR (or CT with increased oxygen requirement): day 5,(record most recent imaging prior to day 5, conducted per standard of care)

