To evaluate the clinical efficacy of CCP relative to the control arm in adults hospitalized with COVID-19 according to clinical status (8-point ordinal scale) at Day 29	
 
Death;
 
Hospitalized, on invasive mechanical ventilation or ECMO;
 
Hospitalized, on non-invasive ventilation or high flow oxygen devices;
 
Hospitalized, requiring supplemental oxygen;
 
Hospitalized, not requiring supplemental oxygen - requiring ongoing medical care (COVID-19 related or otherwise);
 
Hospitalized, not requiring supplemental oxygen - no longer requires ongoing medical care;
 
Not hospitalized, limitation on activities and/or requiring home oxygen;
 
Not hospitalized, no limitations on activities.
 

OBJECTIVES	ENDPOINTS (OUTCOME MEASURES)
Additional Secondary Objectives	

 
To evaluate the clinical efficacy of different investigational therapeutics as compared to the control arm as assessed by:
 
Clinical Severity Ordinal scale:
 
Time to an improvement of one category and two categories from Day 0 (baseline) using an ordinal scale.
 
Subject clinical status using ordinal scale at Days 2,5,8,15, 29
 
Mean change in the ordinal scale from Day 1 to Days 2,5,8,15, 29
 
	
 
Clinical outcome assessed using ordinal scale daily while hospitalized and on Days 15, 29 and 120
 
Time to clinical recovery (defined as ordinal score 1-3)
 

 
National Early Warning Score (NEWS):
 
Time to discharge or to a NEWS of ≤ 2 and maintained for 24 hours, whichever occurs first.
 
Change from Day 1 to Days 2,5,8,15, 29
 
	
 
NEWS assessed daily while hospitalized
 

 
Oxygenation:
 
Oxygenation use up to Day 120.
 
Incidence and duration of new oxygen use during the study.
 
Oxygen requirement on day 1,2,5,8,15, 29
 
	
 
Days of supplemental oxygen (if applicable) up to Day 29
 
PaO2/FiO2 ratio or SpO2/FiO2
 
O2 requirement at day 120
 

 
Non-invasive ventilation/high flow oxygen:
 
Non-invasive ventilation/high flow oxygen use up to Day 29.
 
Incidence and duration of new non-invasive ventilation or high flow oxygen use during the study.
 
	
 
Days of non-invasive ventilation/high flow oxygen (if applicable) up to Day 29
 

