# 5 INVESTIGATIONAL PLAN:

# 5.1 Study objectives

OBJECTIVES	ENDPOINTS (OUTCOME MEASURES)
Primary Objective	
Evaluate the efficacy of convalescent fresh frozen plasma from blood donors who have recovered from Covid-19 containing antibodies to SARS-CoV-2 versus control (standard fresh frozen plasma) to prevent mechanical intubation within 14 days of CPP administration in hospitalized patients with COVID-19 who are within 3 days of hospital admission or 14 days of symptom onset.	Progression to mechanical intubation or death within the first 14 days of enrollment. A secondary endpoint will evaluate progression to endpoint within the first 28 days of enrollment.
Key Secondary Objectives	
To evaluate the clinical efficacy of CCP relative to the control arm in adults hospitalized with COVID-19 according to clinical status (8-point ordinal scale) at Day 29	
 
Death;
 
Hospitalized, on invasive mechanical ventilation or ECMO;
 
Hospitalized, on non-invasive ventilation or high flow oxygen devices;
 
Hospitalized, requiring supplemental oxygen;
 
Hospitalized, not requiring supplemental oxygen - requiring ongoing medical care (COVID-19 related or otherwise);
 
Hospitalized, not requiring supplemental oxygen - no longer requires ongoing medical care;
 
Not hospitalized, limitation on activities and/or requiring home oxygen;
 
Not hospitalized, no limitations on activities.
 

OBJECTIVES	ENDPOINTS (OUTCOME MEASURES)
Additional Secondary Objectives	

 
To evaluate the clinical efficacy of different investigational therapeutics as compared to the control arm as assessed by:
 
Clinical Severity Ordinal scale:
 
Time to an improvement of one category and two categories from Day 0 (baseline) using an ordinal scale.
 
Subject clinical status using ordinal scale at Days 2,5,8,15, 29
 
Mean change in the ordinal scale from Day 1 to Days 2,5,8,15, 29
 
	
 
Clinical outcome assessed using ordinal scale daily while hospitalized and on Days 15, 29 and 120
 
Time to clinical recovery (defined as ordinal score 1-3)
 

 
National Early Warning Score (NEWS):
 
Time to discharge or to a NEWS of ≤ 2 and maintained for 24 hours, whichever occurs first.
 
Change from Day 1 to Days 2,5,8,15, 29
 
	
 
NEWS assessed daily while hospitalized
 

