# 6.2.2 Secondary endpoint (clinical status):

We will evaluate the clinical efficacy of CCP relative to the control arm in adults hospitalized with COVID-19 according to clinical status (8-point WHO ordinal scale) using a proportional odds model. Because clinical status is evaluated on multiple days, we will use a generalized estimating equations (GEE) approach to account for repeated measures within each patient. Changes in ordinal scale at each timepoint will be summarized by proportions.

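### The sections disagree on whether Day 2, 5 and 8 ordinal scores are taken after discharge; if only inpatients are scored, the repeated-measures analysis dilutes a true benefit

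*Combined protocol and SAP*

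**What the plan says.** All references are to the combined protocol and SAP.

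- **Collection limited to inpatients.** In the Section 5.4 day-by-day procedures, the heading "Day 2-15 (if remain hospitalized" covers the item "Assessment of clinical status (8-point ordinal scale) (days 2,5,8". The endpoint column of the objectives tables in Sections 3 and 5.1 reads "Clinical outcome assessed using ordinal scale daily while hospitalized and on Days 15, 29 and 120". No contact with a discharged patient is described before Day 15.
- **Collection without that limit.** The objective in the same tables asks for "Subject clinical status using ordinal scale at Days 2,5,8,15, 29". In Table 1 the row "Assessment with 8- point ordinal scale" is marked on Days 2, 5, 8, 15, 29 and 120. It lacks footnote 2, "If still hospitalized", which is attached to vital signs, oxygenation, laboratory tests and the later swabs and blood samples.
- **After discharge.** The scale is assessed on Day 15 (by phone if the patient has left hospital) and on Day 29 (in person or by phone).
- **Analysis.** Section 6.2.2 compares the arms "according to clinical status (8-point WHO ordinal scale) using a proportional odds model", with GEE for the repeated measures. It adds: "Changes in ordinal scale at each timepoint will be summarized by proportions". It does not list the days that enter the model, and it has no rule for patients who are discharged, dead or otherwise unscored.

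**The concern.** On the WHO scale printed at the end of Section 5.4, scores 1 and 2 are the ambulatory levels and 8 is death. If scores before Day 15 are taken only in hospital, a patient who goes home on Day 4 has no Day 5 or Day 8 score, precisely because that patient reached a good level. A patient who dies on Day 4 is also unscored, although the score is known.

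Missingness then depends on the outcome, and unweighted GEE on available data is not protected against that. The arm that sends more patients home early loses more of its best scores. The early per-day proportions would have inpatients as their denominator, so they would no longer compare the randomised groups. At stake are the repeated-measures analysis of the key secondary scale and the Day 2, 5 and 8 summaries. The primary endpoint is not involved.

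**Working it through.** **1. The plan's own figure.** Section 6.1 states 80% power for the ordinal scale with 25 per arm and two-sided 0.05. Its table, worst to best, is control 12/0/20/12/0/24/16/16% and active 0/0/0/8/20/12/28/32%.

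- The fitted proportional odds ratio in favour of active is 3.51 (log 1.2552).
- Whitehead formula: V = (N/12)(1 - Σp̄³). The averaged proportions are 6/0/10/10/10/18/22/24%, so Σp̄³ = 0.0335, V = (50/12)(0.9665) = 4.027 and √V = 2.007.
- Power = Φ(1.2552 × 2.007 - 1.96) = Φ(0.559) = 71%. Simulated Mann-Whitney power is 68-69%.
- A one-sided test gives 80-81% and a two-sided t-test on the scores gives 82%. The stated 80% is therefore not reproduced with the planned type of test at two-sided 0.05. The present point does not depend on this.

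**2. Mechanism on that table.** Out of hospital: control 16 + 16 = 32%, active 28 + 32 = 60%. Removing them leaves 0.68 × 25 = 17 control and 0.40 × 25 = 10 active patients. The odds ratio moves from 3.51 to 3.26, and Mann-Whitney power from about 68% to 34%. The table has no stated day and this is a single-day test, so the result shows only how the loss works.

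**3. Five-day illustration.** The documents give no discharge rates by Day 2, 5 or 8, so trajectories were assumed:

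- Latent severity is 2.2 - g·ln(day/2) + u - b·arm·ln(day)/ln(29) + e, with u normal (SD 2) and e logistic (scale 0.5).
- It is cut at -2.5, -1, -0.2, 2.0, 3.2, 3.6 and 4.0 into scores 1 to 8.
- There are 200,000 patients per arm, with recovery speed g = 0.8, 1.2 or 1.6 and b = 2.0 (benefit) or 0 (none).
- Day 2, 5 and 8 scores of 1 or 2 are deleted; Days 15 and 29 are complete.
- The model is proportional odds, pooled under working independence without a day term.

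| g | Out of hospital on Day 8, control / active | Day 5 OR, all → inpatients | Day 8 OR, all → inpatients | Five-day pooled OR, all → available |
|---|---|---|---|---|
| 0.8 | 17% / 35% | 2.10 → 1.79 | 2.63 → 2.05 | 2.38 → 2.25 |
| 1.2 | 24% / 45% | 2.09 → 1.75 | 2.59 → 1.93 | 2.22 → 2.06 |
| 1.6 | 33% / 55% | 2.12 → 1.71 | 2.60 → 1.85 | 2.07 → 1.90 |

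On Day 2 the change is small (1.36-1.38 → 1.31-1.33). As a share of the log odds ratio, the Day 8 loss runs from 1 - ln 2.05/ln 2.63 = 26% to 1 - ln 1.85/ln 2.60 = 36%. The pooled loss runs from 1 - ln 2.25/ln 2.38 = 6% to 1 - ln 1.90/ln 2.07 = 12%. With b = 0 every odds ratio stays at 0.99-1.00.

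Limits of the illustration: deaths are kept in, out-of-hospital status is set day by day, and the odds ratios are large-sample values with no power attached.

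**The case against.** **The restriction is not settled.** Table 1 and the objective name Days 2, 5 and 8 without it. If sites follow Table 1, discharged patients are scored and the gap closes. This stands, and it is why the first request is to reconcile the sections. It does not remove the problem, because Section 5.4 and the endpoint column say otherwise and Section 6.2.2 has no fallback rule.

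**The days in the model are an inference.** Section 6.2.2 names none. Including Days 2, 5 and 8 follows from the objective and from the reference to repeated measures. This stands.

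**Stronger readings that the documents do not support:**

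- *Early recoverers leave the model altogether.* They do not. They keep Day 1 and their in-hospital scores, and they are scored again on Days 15 and 29.
- *Power halves, or worse.* A reader might take 68% to 34% from the Section 6.1 table as the loss. If a true proportional odds ratio of 3.5 is applied to that table's control column, the odds ratio falls to about 1.9 and power from 68% to 12-13%. But the table carries no day, the test is single-day and the planned model is not. If the table describes Day 15 or 29, this rule leaves nobody unscored.
- *Time to recovery and time to improvement are also compromised.* The endpoint column calls for daily scores in hospital, and discharge dates can be had from the hospitalization data. Discharge is score 1 or 2, which meets the recovery definition (1-3) and is at least a two-category gain from a baseline of 4 or 5.

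**Conclusion.** The point holds as a conflict between sections with a predictable consequence. Under the in-hospital rule, the available-case GEE and the per-day proportions understate a true benefit whenever plasma speeds discharge. They are not expected to create a false one.

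The size is moderate and depends on early discharge rates that the documents do not give. In the assumed scenarios the dilution is marked on Day 8 (odds ratio about 2.6 to 1.85-2.05) and smaller once Days 15 and 29 are pooled in (2.07-2.38 to 1.90-2.25). A comparison at Day 29 alone, the key secondary time point, is unaffected; it is touched only if a single treatment effect is pooled over days. The conclusion assumes that Days 2, 5 and 8 enter the model and that unscored days are left missing.

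**What to change.** 1. Reconcile the endpoint column in Sections 3 and 5.1, Table 1 and the Day 2-15 procedures in Section 5.4, so that all give the same rule for scoring after discharge.
2. In Section 6.2.2, list the days that enter the GEE.
3. Add a scoring rule for every patient in the modified intention-to-treat set of Section 6.2.1. Patients discharged alive are scored as not hospitalized on Days 2, 5 and 8 unless readmitted, with levels 1 and 2 merged on those days where no call is made. Death is carried forward as 8. Use the same denominators for the per-day proportions.
4. Fix the rule before unblinding, and state how any remaining missing scores are handled, with a sensitivity analysis.

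The cost is wording. Days of hospitalization and date of death are already planned data, so no new visit is needed. The small downside is that levels 1 and 2 are not separated on the early days.

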# Day 15 (phone contact if no longer hospitalized or if in person visit is not feasible )

- 1.COVID-19 symptom screen (fevers, cough, shortness of breath)
- 2. Assessment of clinical status (8-point ordinal scale) & WHO 11 point scale[27] (added to facilitate data analysis across data sets)
- 3. New medical conditions, AE evaluation, concomitant medications
- 4.Oxygenation status: current FiO2 or liters of O2, route of oxygen, and oxygen saturation or PaO2 (if available)
- 5. CBC, comprehensive metabolic panel, inflammatory markers (if seen in person)
- 6. Serological testing: anti-SARS CoV-2 antibody levels if hospitalized
- 7. Nasopharyngeal or mid-turbinate nasal swabs with OP swab if possible (if seen in person)
- 8. CXR (or CT with increased oxygen requirement): day 15,(record most recent imaging prior to day 15, conducted per standard of care)
- 9. Stored samples for future studies(3 EDTA, 1 SST) (if seen in person)

# Day 29: (in person visit if feasible, phone contact if not)

1. COVID-19 symptom screen (fevers, cough, shortness of breath)

2. Assessment of clinical status (8-point ordinal scale) & WHO 11 point scale[27] (added to facilitate data analysis across data sets)

3. Oxygenation status: current FiO2 or liters of O2, route of oxygen, and oxygen saturation or PaO2 (if available)

4. New medical conditions, AE evaluation, concomitant medications (only recorded if treatment given for COVID-19 after day 15)

5. CBC, inflammatory markers (if seen in person)

6. Blood for stored testing, if feasible (3 EDTA, 1 SST)This will include serological testing for SARS CoV-2 antibodies

# Day 120 In-person (if feasible)

- 1. COVID-19 symptom screen (fevers, cough, shortness of breath)
- 2. Assessment of clinical status (8-point ordinal scale)
- 3. New medical conditions, AE evaluation
- 4. Serological testing: anti-SARS CoV-2 antibody levels

5. Blood for stored testing, if feasible (3 EDTA, 1 SST). This will include serological testing for SARS CoV-2 antibodies

# 8 point WHO ordinal Scale of clinical status[28]

# **Ordinal Scale for Clinical Improvement**

Patient State	Descriptor	Score
Uninfected	No clinical or virological evidence of infection	0
Ambulatory	No limitation of activities	1
	Limitation of activities	2
Hospitalized Mild disease	Hospitalized, no oxygen therapy	3
	Oxygen by mask or nasal prongs	4
Hospitalized Severe Disease	Non-invasive ventilation or high-flow oxygen	5
	Intubation and mechanical ventilation	6
	Ventilation + additional organ support – pressors, RRT, ECMO	7
Dead	Death	8

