
 
Invasive Mechanical Ventilation / extracorporeal membrane oxygenation (ECMO):
 
Ventilator / ECMO use up to Day 29.
 
Incidence and duration of new mechanical ventilation or ECMO use during the study.
 
	
 
Days of invasive mechanical ventilation/ECMO (if applicable) up to Day 29.
 

 
Hospitalization
 
Duration of hospitalization (days).
 
	
 
Days of hospitalization as of Day 29 and day 120
 

Mortality 
 
15-day mortality
 
29-day mortality
 
120-day mortality
 
	
 
Date and cause of death (if applicable)
 

To evaluate the safety of CCP as compared to the control arm as assessed by:	• SAEs

 
Cumulative incidence of SAEs through Day 29.
 
Cumulative incidence of Grade 3 and 4 clinical and/or laboratory AEs through Day 29.
 
Transfusion associated adverse events
 
	
 
Grade 3 and 4 AEs
 
Grade 2 or higher AE's attributed to CCP
 

 
Exploratory Objectives
 
To evaluate the virologic efficacy of CCP
 
	

 
as compared to the control arm as assessed by:
 
Percent of subjects with SARS-CoV-2 detectable in nasal sample at Days 1,5,8,15
 
Quantitative SARS-CoV-2 virus in NP/MTN sample at Days 1,2,5,8,15
 
	
 
Qualitative and quantitative polymerase chain reaction (PCR) for SARS-CoV-2 in NP/MTN swab on Day 1,2,5,8,15 (while hospitalized)
 

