#### 11 point WHO ordinal Scale[27]

- 0: Uninfected, no viral RNA detected
- 1. Asymptomatic, viral RNA detected
- 2. Symptomatic, independent
- 3. Symptomatic, assistance needed
- 4. Hospitalized, no oxygen therapy
- 5. Hospitalized, oxygen by mask or nasal prongs
- 6. Hospitalized, oxygen by non-invasive ventilation or high flow
- Intubation & Mechanical ventilation, pO2/FIO2 ≥ 150 or SpO2/FIO2 ≥ 200
- Mechanical ventilation, pO2/FIO2 < 150 (SpO2/FIO2 < 200) or vasopressors

- 9. Mechanical ventilation, pO2/FIO2 < 150 and vasopressors, dialysis or ECMO
- 10. Dead

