Not hospitalized, no limitations on activities.	16%	32%

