# 6.2 Statistical Analysis

# 6.2.1 **Primary endpoint**

Our primary hypothesis is that by providing anti-SARS-CoV-2 plasma, the rate of progression to mechanical ventilation or death will be decreased as compared to the rate in in the group receiving control plasma. We will apply a Fisher exact test to compare the combined endpoint of mechanical ventilation/death respiratory failure rates between the two groups occurring by day 15. 29. All analyses

will be conducted with a modified intention-to-treat approach, which excludes randomized subjects who do not initiate an infusion of the study plasma. As secondary analysis, we will also analyze the reduced oxygenation rate, requirement for supplemental oxygen rate, length of hospitalization, time to recovery (ordinal score 1-3) and mechanical ventilation rate, respectively, as well as occurrence of the primary endpoint by day 29 Statistical inference will be based on a two-sided Type 1 error rate of 0.05 and 95% confidence intervals.

Participants who are intubated for reasons other than hypercarbia/hypoxia, such as for a procedure or airway obstruction, will have ventilation settings evaluated to determine if need for ventilation due to hypoxia is meet. This will be determined by >12 hours of requirement for a mandatory mode of ventilation (volume control or pressure control) or Fi02 of > 40%. External adjudication of intubation for non-hypoxic/hypercarbic indication will be conducted.

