# 6.2.6 Analysis the rates, levels and duration of SARS-CoV-2 RNA in NP/MTN swabs

This secondary analysis will be primarily descriptive. The proportion positive at days 1,2,5,8, and 15 and whether individuals lose positivity status at a subsequent visit among those who were initially positive will be examined. To determine the proportion that are positive at each visit, we will do a pooled complementary log-log model in order to describe the cumulative incidence of SARS-CoV-2 positivity over time. The pooled complementary log-log model is a discrete time-to-event-analysis that estimates the log hazard rate at each discrete time point. Similar to the analysis of anti-SARS-CoV-2 antibody levels, the goal of this secondary aim is to describe the distribution of SARS-CoV-2 RNA between randomized arms. Therefore, we will use the same approach as that for the anti-SARS-CoV-2 antibody levels. Because the exact day that an individual becomes negative is not known, a minimum and maximum amount of positive time will be used to describe the positive duration of each individual. If the sample is adequate, we will describe the duration of positivity using a non-parametric approach for time-to-event analysis.

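### The scored 8-point scale has a virology-dependent level 0 that mostly cannot be observed after discharge and lies outside the recovery range of 1 to 3 (minor)

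*Combined protocol and SAP*

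**What the plan says.** All references are to the combined protocol and SAP.

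- **Scale.** The scored table in section 5.4 is titled as an 8-point scale but prints scores 0 to 8. Score 0 is "No clinical or virological evidence of infection"; score 1 is an ambulatory patient without activity limits. Section 6.2.2 names the 8-point WHO scale for the proportional-odds analysis.
- **Recovery.** The objectives tables in sections 3 and 5.1 give "Time to clinical recovery (defined as ordinal score 1-3"; section 6.2.1 repeats it as "time to recovery (ordinal score 1-3". None of the three includes 0.
- **Virology.** The exploratory endpoint is PCR for "SARS-CoV-2 in NP/MTN swab on Day 1,2,5,8,15 (while hospitalized", and section 6.2.6 analyses "The proportion positive at days 1,2,5,8, and 15". Table 1 makes the Day 5, 8 and 15 swabs conditional on still being in hospital, and its footnote adds "Collect on day 5, 8, 15 if feasible". The Day 15 visit may be a phone contact, with a swab only if the patient is seen in person. The Day 29 and Day 120 lists include the 8-point scale but no swab.
- **Frequency of scoring.** The objectives tables say daily in hospital, then Days 15, 29 and 120. Table 1 and the day-by-day procedures give Days 2, 5 and 8, then 15, 29 and 120.
- **Other lists.** The section 6.1 planning table has eight rows, the best being "Not hospitalized, no limitations on activities". The objectives tables also list eight categories. Neither has an uninfected state.

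**The concern.** The patients who could score 0 are those who have gone home well, and they are the ones least likely to have a swab. Nothing in the plan says whether such a patient scores 0 or 1 when no swab exists, so the choice falls to the rater. The recovery rule then treats the two scores differently: 1 is recovered and 0, taken literally, is not. Recovery is a named secondary analysis, and the score is also averaged for mean change. An undefined coding choice among the best-doing patients could therefore move both results.

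**Working it through.** **1. The stated figure tied to the scale.** Section 6.1 claims 80% power for the ordinal comparison with 25 per arm. Simulating its two columns gives 80.6% with a two-sided t-test on the scores and 79.1% with a one-sided 0.05 Wilcoxon test, but 68.2% with the two-sided Wilcoxon test and 68.0% with a proportional-odds likelihood-ratio test. The gap from 80% is a separate matter; 68.2% is the reference for step 6.

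**2. What can be observed.**

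| Day | 8-point scale | Study swab |
|---|---|---|
| 2 | scored | yes, in hospital |
| 5, 8 | scored | if still in hospital and feasible |
| 15 | scored, by phone if discharged | if in hospital (Table 1) or seen in person (Day 15 list) |
| 29 | scored, by phone if no visit | none listed |
| 120 | scored | none listed; serology only |

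Level 0 cannot be told from level 1 by study virology at Days 29 and 120, and mostly not at Day 15 after discharge.

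**3. Time to recovery.** Take a patient on oxygen by nasal prongs at Day 8 (score 4), sent home before Day 15 and reached by phone, well, at Day 15.
- Scored 1: recovery is recorded at Day 15.
- Scored 0 then and afterwards: no score of 1 to 3 is ever recorded, and the literal rule never counts recovery.
- Under daily in-hospital scoring, the same patient would count earlier if seen off oxygen before discharge (score 3).

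The documents give no distribution of such paths, so the number affected cannot be computed.

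**4. Time to one- or two-category improvement.** Everyone enters in hospital, so baseline is 3 or higher. From 3, a one-category improvement needs 2 or lower and a two-category improvement needs 1 or lower. Scores 0 and 1 meet both; from a higher baseline the same holds. The split has no effect.

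**5. Mean change.** Score the section 6.1 rows 8 (death) down to 1 (no limitations).
- Control: 8(0.12) + 6(0.20) + 5(0.12) + 3(0.24) + 2(0.16) + 1(0.16) = 3.96.
- CCP: 5(0.08) + 4(0.20) + 3(0.12) + 2(0.28) + 1(0.32) = 2.44.
- Difference: 3.96 − 2.44 = 1.52.

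Let f be the share of no-limitation patients scored 0, the same in both arms (an assumption). The means become 3.96 − 0.16f and 2.44 − 0.32f, and the difference 1.52 + 0.16f. At f = 0.5 it is 1.60; at f = 1 it is 3.80 − 2.12 = 1.68. With equal baseline means this is also the difference in mean change. It moves in favour of CCP.

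**6. Rank comparison.** Two-sided Wilcoxon power is 68.2% unsplit (20,000 simulations), 67.4% with a random half of the top level scored 0, and 68.4% with all scored 0 (8,000 each). These differ by no more than simulation error. The split was run with the rank test, not the repeated-measures model.

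**7. Illustration only: recovery as status on one day.** Scores 1 to 3 total 16 + 16 + 24 = 56% (control) and 32 + 28 + 12 = 72% (CCP). With share f scored 0 these become 56 − 16f and 72 − 32f.

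| f | Control | CCP | Difference |
|---|---|---|---|
| 0 | 56% | 72% | 16 points |
| 0.25 | 52% | 64% | 12 |
| 0.5 | 48% | 56% | 8 |
| 0.75 | 44% | 48% | 4 |
| 1 | 40% | 40% | 0 |

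**The case against.** The best defence is that level 0 was never meant to be used. The scale is called 8-point, and both the objectives list and the section 6.1 table have eight states with no uninfected level. Numbered from the best state, the objectives list makes 1 to 3 its three best categories, so adopting it would remove the problem. That is true. But those lists print no scores, the only scored version prints a 0, and section 6.2.2 names the WHO scale. The intention needs to be written down.

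A second defence is that every participant is a confirmed case, so a rater without a swab has no positive ground for calling one uninfected and would choose 1. That is plausible, but absence of evidence can equally be read as satisfied when no test was done. The text does not decide.

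Third, with daily in-hospital scoring most patients would pass through 3 before going home. This stands and shrinks the effect on time to recovery. It does not remove it, because Table 1 and the procedures schedule scoring only on Days 2, 5 and 8 before Day 15.

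A reader might infer from step 7 that the recovery benefit disappears. The documents do not support that. Recovery is planned only as a time to event, not as status on a day. The planning table prints no day, and its CCP column is a detectable difference, not an expected result. The zero difference also needs every no-limitation patient to be scored 0. Nor does the point extend to the 11-point scale: its lowest level, "0: Uninfected, no viral RNA detected", also turns on RNA, but section 6.2 plans no analysis of that scale, which was added for use across data sets.

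**Conclusion.** The point holds and is minor. As written, the scored scale has a best level that the trial mostly cannot distinguish from the next one, and the recovery rule leaves that level out.

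Two secondary results are exposed:
- **Time to recovery**, for patients who reach 0 with no recorded 1 to 3. The size is unknown: appreciable only under the sparser scoring schedule, and small under daily scoring.
- **Mean change**, where the difference between arms lies between 1.52 and 1.68 on the section 6.1 columns. This assumes the same coding habit in both arms and equal baseline means.

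The primary endpoint does not use the scale. The ordinal comparison is essentially unchanged, and time to one- or two-category improvement is unchanged.

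**What to change.** In section 6.2 and in the scale table, merge scores 0 and 1 into one lowest level, out of hospital without activity limits. This matches the eight rows in section 6.1. Then define recovery, in sections 3, 5.1 and 6.2.1, as a score of 3 or lower so that this level counts. Leave the 11-point scale as it is.

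The cost is one sentence of plan wording, repeated where recovery is defined, and one recode. What is lost is a 0 versus 1 distinction that the trial mostly cannot measure.
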